7.2. Laboratory Evaluations

Laboratory data will be listed.

7.2.1. Graded Laboratory Values

There are no plans to assign toxicity grade to clinical laboratory results in this study. A separate listing of treatment-emergent laboratory abnormalities will be provided. Treatment-emergent laboratory abnormalities are defined as values that are normal at baseline (on or within the reference range bounds) and abnormal post-baseline (outside of the reference range bounds).

If the baseline value is missing and the post-baseline value is abnormal, the abnormality will be considered treatment-emergent. Laboratory abnormalities during the screening visit will be included in the laboratory data listings only.

Laboratory abnormalities may be reported as AEs, and as such the investigator will assign severity grade to each, and the events will be included in the AE summaries.

7.3. Body Weight and Vital Signs

Vital signs and body weight at each visit and their change from baseline values will be summarized for the safety analysis set using descriptive statistics (sample size, mean, standard deviation, median, Q1, Q3, minimum, and maximum) by treatment group for each post-baseline analysis visit. Baseline body weight and height will be summarized in the baseline and demographics table. The vital signs listing will include body weight, height, BMI, blood pressure, respiratory rate, and pulse.

7.4. Vital Signs from CPET

Vital signs are collected as part of the CPET. The vital sign values from the CPET (resting, peak, and 2-minute recovery) will be presented in the listings.

7.5. Prior Medications

Prior medications are defined as any medications taken before a subject took the first study drug. Prior medications will be coded using the World Health Organization (WHO) Drug Dictionary. The WHO preferred name and Anatomical Therapeutic Chemical (ATC) code and classes will be attached to the clinical database.

Any medication with a start date prior to the first dosing date of study drug will be classified as a prior medication regardless of when the stop date is. If a partial start date is entered the medication will be considered prior unless the month and year (if day is missing) or year (if day and month are missing) of the start date are after the first dosing date. Medications with a completely missing start date will be classified as prior medications.

7.6. Concomitant Medications

Concomitant medications are defined as medications taken while a subject took study drug. Concomitant medications will be coded using the WHO Drug Dictionary. The WHO preferred name and drug code will be attached to the clinical database.

Any medications with a start date prior to or on the first dosing date of study drug and continued to be taken after the first dosing date, or started after the first dosing date will be considered concomitant medications. Medications started and stopped on the same day as the first dosing date will also be considered concomitant. Medications with a stop date prior to the date of first dosing date of study drug will not be considered concomitant medications. If a partial stop date is entered, any medication with the month and year (if day is missing) or year (if day and month are missing) prior to the date of first study drug administration will not be classified as concomitant medications. Medications with completely missing start and stop dates will be considered concomitant medications.

Prior and concomitant medications will not be summarized. All prior and concomitant medications (other than per-protocol study drugs) will be provided in a by-subject listing sorted by subject ID number and administration date in chronological order.

7.7. Electrocardiogram Results

The following analyses of 12-lead ECG results are intended to identify gross changes in QT interval and other ECG characteristics. If potential abnormalities of interest are identified, further analyses may be conducted. Summaries of continuous ECG results (RR, PR, QRS, QT, and QTcB) will be provided for the safety analysis set using descriptive statistics (sample size, mean, standard deviation, median, Q1, Q3, minimum, and maximum) by treatment group for each post-baseline analysis visit.

7.7.1. Corrected QT Intervals

The QT interval (measured in msec) will be corrected for heart rate as indicated in Section 3.7 using Bazett's formula.

QTcB, and uncorrected QT values at each visit and change from baseline at each visit will be summarized for the safety analysis set by treatment group using descriptive statistics (sample size, mean, standard deviation, median, Q1, Q3, minimum, and maximum).

7.7.2. Prolonged QT Intervals and QT, PR and QRS Intervals

The number (%) of subjects with core laboratory ECG values, and change from baseline in the ranges shown in the table below will be summarized by treatment group at each visit.

PR Interval (msec)	QRS Interval (msec)	QT _c B (msec)	QT _c B Change from Baseline (msec)
< 200	< 120	> 450	< -60
≥ 200	≥ 120	≥ 480	≥ -30
≥ 220		≥ 500	≥ 0
			≥ 30
			≥ 60

Categorical ECG abnormalities (borderline and prolonged QTcB, PR ≥ 200, PR ≥ 220, QRS ≥ 120, QTcB > 450, QTcB ≥ 480, QTcB ≥ 500, QTcB change from baseline ≥ 30, QTcB change from baseline ≥ 60) will be flagged in the corresponding listing.

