Safety: Safety will be assessed by the incidence of treatment-emergent AEs, (including physical exam findings new from baseline), death, appropriate ICD interventions (shock or anti-tachycardia pacing) in subjects with ICDs, and clinically significant abnormalities in vital signs, laboratory parameters, arrhythmia burden, and ECG variables.

Efficacy: The primary endpoint of this study is the change in Peak VO₂ between Screening (baseline) and Week 24.

The secondary endpoints of this study include:

- Change in MLHFQ from baseline to Week 24.
- Change in treadmill exercise time from baseline and to Week 24.
- Change in Peak VO₂ from baseline to Week 12.
- Change in the MLHFQ from baseline to Week 12.
- Change in treadmill exercise time from baseline to Week 12.

The exploratory endpoints of this study include:

Statistical Methods:**Randomization:**

Following successful completion of the Screening and Randomization assessments, eligible subjects will be randomized in a 1:1 ratio to 30 mg single loading dose followed by 3 mg maintenance dose of GS-6615 until Week 12 then 6 mg daily maintenance dose of GS-6615 from Week 12 to at least Week 24, or matching placebo. Randomization will be stratified by sex and by age (≥ 50 years and < 50 years).

Timing of Analyses:

After all subjects have completed the double-blind treatment period (including the 30-day follow-up visit for subjects not continuing in the open-label extension), the database will be cleaned and locked for the primary analysis of efficacy and safety for the double-blind treatment period.

At the end of the study (ie, after all subjects have completed the open-label extension period including the 30-day follow-up visit), the database will be cleaned and locked for the secondary analysis of safety and PK data collected during the open-label extension period.

Efficacy Analysis Specifications:

Baseline is defined as the Randomization visit value, if available, otherwise the Screening visit value serves as baseline.

The primary endpoint is the change in Peak VO_2 between the Screening and the Week 24 visits. The treatment effect of GS-6615 compared to placebo will be evaluated using analysis of covariance (ANCOVA) including terms for treatment, sex, age (as a continuous variable), and Peak VO_2 at baseline.

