3.8.2. Analysis Windows

Subject visits might not occur on protocol-specified days. Therefore, for the purpose of analysis, observations will be assigned to visits based on the windows presented in Table 3-1. Day 1 is the day of first dose of study drug.

Table 3-1. Visit Windows for Peak VO₂, MLHFQ, Treadmill Exercise Time, Biomarker Data, CPET 12-Lead ECG, and ICD Interrogation

Visit	Target Day	Visit Window in Day(s)
Baseline		≤ 1
Week 12	84	2–126
Week 24	168	> 126

Table 3-2. Visit Windows for ECHO

Visit	Target Day	Visit Window in Day(s)
Baseline		≤ 1
Week 2	14	2-49
Week 12	84	50–126
Week 24	168	> 126

Table 3-3. Visit Windows for Arrhythmia Burden

Visit	Target Day	Visit Window in Day(s)
Baseline		< 1
Days 1–14	1	1–21
Weeks 6–8	42	22–84
Weeks 18–20	126	> 84

The target and window are based on the start date of the 14-day ZIO[®] XT Patch period.

Table 3-4. Visit Windows for 12-Lead ECG, Vital Signs, and Clinical Laboratory Data

Visit	Target Day	Visit Window in Day(s)
Baseline		≤ 1
Week 2	14	2–28
Week 6	42	29–63
Week 12	84	64–105
Week 18	126	106–147
Week 24	168	148–210
Week 36	252	211–294
Week 48	336	295–378
Week 60	420	379–462
Week 72	504	463–546
Week 84	588	> 546 – last dose date + 30 days

All visits, including Unscheduled, Early Termination, and Follow-up visits, will be eligible for inclusion in table summaries based on the windows presented in Table 3-1, Table 3-2, and Table 3-3.

In the efficacy summary tables, Peak VO₂, treadmill exercise time, MLHFQ, ECHO, QTc interval at rest and at Peak from the exercise ECG, and biomarker results will be summarized based on values obtained at the visit using the windows in Table 3-1 or Table 3-2.

For the safety summaries, all visits other than the Follow-up visit, including Unscheduled and Early Termination visits, will be eligible for inclusion in table summaries based on the windows presented in Table 3-4.

In the safety summary tables for 12-lead ECG and vital signs, data obtained after the last dose date plus 30 days will be excluded from the summaries, but will be included in the listings.

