3.8.3. Selection of Data in the Event of Multiple Records in a Window

Depending on the statistical analysis method, single values may be required for each analysis window. A single value will be chosen based on the rules below.

If multiple nonmissing numeric observations exist in a window, a record will be chosen based on the following rules:

- For baseline, the last available record on or prior to the date of the first dose of study drug will be selected. If there are multiple records with the same time or no time recorded on the same day, average (arithmetic or geometric mean, as appropriate) will be used for the baseline value.
- For post baseline assessments:
 - The record closest to the target day for that visit will be selected.
 - If there are 2 records equidistant from the target, the later record will be selected.
 - If there is more than 1 record on the selected day, the average will be taken, unless otherwise specified.

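### SAP 7.7.2 counts ECG outliers by arm only at each visit, so no table gives the number of subjects per arm who ever crossed a PR, QRS or QTcB threshold or who newly crossed one

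*SAP*

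**What the plan says.** The protocol synopsis (Criteria for Evaluation) bases safety partly on "clinically significant abnormalities in vital signs, laboratory parameters, arrhythmia burden, and ECG variables". Protocol 8.1.5 lists PR, RR, QRS, QT and QTc among the safety endpoints.

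SAP 7.7.2 carries this out as a table of categories: PR ≥ 200 and ≥ 220 msec, QRS ≥ 120, QTcB > 450, ≥ 480 and ≥ 500, and bands of QTcB change that include ≥ 30 and ≥ 60. The counts are made by arm: the values and "change from baseline in the ranges shown in the table below will be summarized by treatment group at each visit". The same section flags the abnormal categories in a listing. SAP 7.7.3 is a listing only, and SAP 7.10 drops the summary of overall ECG assessments.

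Two further rules bear on which ECGs reach the table:

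- SAP 3.8.2: "For the safety summaries, all visits other than the Follow-up visit, including Unscheduled and Early Termination visits, will be eligible for inclusion" in the tables built on the Table 3-4 windows. Data later than 30 days after the last dose are left out of the ECG summaries.
- SAP 3.8.3 opens with a condition: "Depending on the statistical analysis method, single values may be required for each analysis window". Where that holds, for post-baseline data, "The record closest to the target day for that visit will be selected". The later record wins a tie, and records on the same day are averaged.

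For laboratory values, SAP 7.2.1 defines a treatment-emergent abnormality as normal at baseline and abnormal afterwards. The SAP has no such definition for ECG.

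**The concern.** A safety reader wants to know how many subjects in each arm had an outlying ECG at any time on treatment, and how many of those were not outlying at the start. A run of visit-wise percentages answers neither question.

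- **Persistence.** Two visits with two subjects each may involve two people or four. SAP section 2 says the sponsor terminated the trial before the end of the double-blind phase. The number of subjects will therefore differ from visit to visit, and the percentages cannot be combined afterwards.
- **Record selection.** An unscheduled ECG is often taken for a reason. A rule that prefers the record nearest the target day favors the routine tracing.
- **Baseline.** Protocol 4.3 sets no entry limit on PR, QRS or QTc, so subjects already over a threshold can be randomized. In the PR, QRS and absolute QTcB columns they count at each visit exactly as a new crossing does.

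**Working it through.** The plan states no outlier rate or expected count, so there is no figure to reproduce. The check applies the SAP's rules to cases and then bounds the any-time count.

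**Inputs.** The windows come from SAP Table 3-4: Week 2, Days 2–28 (target 14); Week 6, 29–63 (42); Week 12, 64–105 (84); Week 18, 106–147 (126); Week 24, 148–210 (168). The selection rule is SAP 3.8.3, taken here to apply to the 7.7.2 table. The arm size is the planned 90 (SAP 1.3). The QTcB values and outlier rates are assumed.

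**1. Displacement.** Scheduled ECGs fall on the target days, all with QTcB 440, and there is one unscheduled ECG of 505 on Day 100. Days 84 and 100 are both in the Week 12 window. Their distances from target are |84 − 84| = 0 and |100 − 84| = 16, so Day 84 is kept. The subject appears in no > 450, ≥ 480 or ≥ 500 cell at any visit.

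**2. Dilution.** Two ECGs on Day 84 read 440 and 505. The average is (440 + 505)/2 = 472.5. The subject counts as > 450 but not as ≥ 480 or ≥ 500.

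**3. How often displacement could happen.** Assume one scheduled ECG in every window, uniform over the protocol tolerance (±3 days at Week 2, ±7 days otherwise), and one unscheduled ECG uniform over Days 2–210. In 200,000 simulated draws the unscheduled record was displaced 83% of the time. It is kept when it lies nearer the target or is alone in its window.

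**4. Baseline status.** Subject A has QTcB 485 at baseline and throughout. Subject B goes from 440 to 485. Both count as ≥ 480 at each visit. The change column puts B (+45) in ≥ 30 and A (0) not, but the two columns are not cross-classified. PR and QRS have no change column in 7.7.2, and SAP 7.7.1 gives change from baseline only for QT and QTcB.

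**5. Any-time count from visit counts.** Let n = 90, k = 5 visits and p = the rate at each visit.

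- Lower bound (same subjects every time): n × p
- Upper bound (different subjects every time): n × p × k
- Independence between visits: n × [1 − (1 − p)^k]

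| Assumed p | At each visit | Lower | Independence | Upper |
|---|---|---|---|---|
| 1% | 0.9 | 0.9 | 4.4 | 4.5 |
| 2% | 1.8 | 1.8 | 8.6 | 9.0 |
| 5% | 4.5 | 4.5 | 20.4 | 22.5 |

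Every value between the bounds is compatible with the same visit table. The calculation takes full planned enrollment and no drop-out.

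**The case against.** The strongest case on the other side has five parts.

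- **QTcB baseline is handled.** The table has change-from-baseline bands. This stands. A reader might infer that the ECG counts ignore baseline altogether, and for QTcB that is wrong. The gap is confined to PR, QRS and absolute QTcB. The visits tabulated may also include baseline, which Table 3-4 lists as a visit. Even so, marginal counts at baseline and later do not show who crossed.
- **Nothing is lost from the report.** Unscheduled ECGs are expressly eligible and outliers are flagged in the listing. Protocol 6.12 and 7.1.3 route ECG findings into adverse events when they are clinically significant, or come with symptoms, and meet the adverse event definition. SAP 7.1.6 then counts those events once per subject by arm. This also stands, so a reader should not infer that the plan suppresses abnormal ECGs. But a listing is not a per-arm count, and adverse event tables depend on investigator judgment and coded terms, not on the thresholds in 7.7.2.
- **The single-record rule is conditional**, and 7.7.2 does not invoke it. This stands as a limit on certainty. One value per subject per visit is the natural reading of a by-visit table. If something else is meant, 7.7.2 should say so.
- **The size is assumed.** This stands. A reader might infer that true incidence is several times the visit rate, but that needs near-independence between visits. If the same subjects are abnormal each time, the gap is zero.
- **By-visit summary is what the protocol asks for** (8.6.4), the report is synoptic, and SAP 7.7 allows further analyses. This is a fair argument against calling the table an error. The further analyses are discretionary and unspecified, so they do not replace a planned row.

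**Conclusion.** The point holds as a gap in tabulation. The visible text of the SAP gives no per-arm count of subjects who ever crossed a PR, QRS or QTcB threshold, and none of those who newly crossed one on PR, QRS or absolute QTcB. The QTcB change bands of ≥ 30 and ≥ 60 msec are present, but only by visit and not crossed with absolute values.

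Loss or dilution of an abnormal unscheduled or early-termination ECG in the by-arm table depends on SAP 3.8.3 governing that table, which is likely but not stated. The size cannot be fixed from the documents. At an assumed 2% per visit, the number ever affected per arm lies between 1.8 and 9.0, and the planned table cannot narrow that range. The 83% displacement figure rests on the assumed timing of ECGs and is an illustration only.

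This is a low-cost improvement to the safety report. It does not show that the planned table is invalid or that ECG safety goes unreported.

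**What to change.** Keep the by-visit rows in SAP 7.7.2 and add, for each arm:

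1. The number (%) of subjects with any post-baseline core-laboratory ECG from first dose to last dose + 30 days that is over each PR, QRS and QTcB threshold, and with QTcB change of ≥ 30 or ≥ 60 msec. Use scheduled, unscheduled and early-termination ECGs, without the closest-to-target or same-day-averaging rule.
2. For PR, QRS and absolute QTcB, the same count restricted to subjects below the threshold at baseline, with the percentage taken of those subjects.

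State in 7.7.2 which records feed the by-visit rows. State also whether Follow-up visit ECGs within last dose + 30 days count in the new rows, since SAP 3.8.2 keeps that visit out of the safety tables. Protocol 6.6.1 sets the visit at 30 days (+7) after the last dose, so an on-schedule visit falls inside that limit only if held on day 30.

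The cost is a few lines of SAP text and one table panel, with no new data. The new percentages will be at least as high as those at any one visit when the same denominator is used. They rise with the number of ECGs and the length of follow-up per subject, so report both by arm beside the panel.

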7.7.3. Investigator Assessment of ECG Readings

A by-subject listing for ECG assessment results will be provided by subject ID number and visit in chronological order.

7.8. Continuous ECG Results from ZIO[®] XT Patch

Continuous ECG monitoring results from ZIO[®] XT Patch worn during the 14-day baseline period (prior to randomization), Days 1 to 14, Weeks 6 to 8, and Weeks 18 to 20 will be analyzed as indicated in Section 6.5.1.

7.9. Other Safety Measures

The number of subjects who died or who experienced at least 1 adjudicated appropriate ICD intervention (shock or anti tachycardia pacing) will be summarized by treatment group for subjects with an ICD. A data listing will be provided for adjudicated ICD interventions (shocks or anti-tachycardia pacing).

A data listing will be provided for subjects experiencing pregnancy during the study.

7.10. Changes From Protocol-Specified Safety Analyses

Laboratory data, concomitant medication data, vital signs from CPET, and ECG overall assessments will not be summarized.

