1.2.3. Clinical Trials of GS-6615

As of January 2014, a total of 95 subjects have been exposed to GS-6615 across four Phase 1 studies (see below). GS-6615 has demonstrated an acceptable tolerability and safety profile, with no clinically significant changes in vital signs or laboratory parameters. There have been no serious adverse events related to GS-6615 in any of the recently completed or ongoing studies.

Clinical trials of GS-6615 include:

- GS-US-279-0101: A Phase 1 single ascending dose (SAD) study of GS-6615, Study GS-US-279-0101, was conducted in 48 healthy subjects and has been completed. This first-in-human study was a randomized, double-blind, placebo-controlled single ascending oral dose study to evaluate the safety, tolerability, and pharmacokinetics (PK) of GS-6615 in healthy subjects. The study evaluated 6 single oral doses of GS-6615 (3 mg, 10 mg, 20 mg, 30 mg, 40 mg, and 60 mg) in a sequential manner. In general, GS-6615 was well tolerated, and no clinically significant adverse events (AEs) or laboratory findings were observed except for AEs involving transient transaminase elevations in 2 subjects. An alanine aminotransferase (ALT) value of 4 times the upper limit of normal (ULN) was reported in one subject receiving the 30 mg dose of GS-6615. This subject also had symptoms of fatigue, sweats, nausea, and vomiting, which resolved after one day without treatment. An ALT increase > 3x ULN was observed in a second subject receiving placebo who was otherwise asymptomatic. In both subjects, bilirubin levels were normal and ALT returned to baseline within the next few days without clinical sequelae.

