4.3. Exclusion Criteria

Subjects who meet any of the following exclusion criteria are not to be enrolled in this study. During Screening, the subject may have any of the laboratory tests repeated once for confirmation only when medically warranted (eg, suspected laboratory error, inappropriate handling of blood/plasma/serum samples, etc.).

- 1) Known aortic valve stenosis (moderate or severe) confirmed by echocardiogram
- 2) Known coronary artery disease (defined as $\geq 50\%$ stenosis in ≥ 1 epicardial coronary artery)
- 3) Left ventricular systolic dysfunction (ejection fraction $< 50\%$), known or detected during Screening visit
- 4) Known moderate or severe Chronic Obstructive Pulmonary Disease (defined as $FEV_1 < 80\%$ predicted)
- 5) Known moderate or severe restrictive lung disease (defined as total lung capacity $< 70\%$ predicted)
- 6) Recent septal reduction procedure (ie, surgical myectomy or alcohol septal ablation) within six months prior to Screening or such a procedure scheduled to occur during the study
- 7) Atrial fibrillation on 12-lead ECG at Screening or detected during Randomization visit. Subjects with paroxysmal atrial fibrillation in whom sinus rhythm is restored may be re-screened at a later date.
- 8) Known or suspected infiltrative myocardial disease or glycogen storage disorder
- 9) Body mass index (BMI) $\geq 36 \text{ kg/m}^2$
- 10) Severe renal impairment at Screening (defined as an estimated GFR $< 30 \text{ mL/min/1.73m}^2$ as calculated by the Modification of Diet in Renal Disease [MDRD] equation by the central laboratory)
- 11) Abnormal liver function tests at Screening, defined as ALT or AST $> 2x$ ULN, or total bilirubin $> 1.5x$ ULN
- 12) Known or suspected history of seizures or epilepsy
- 13) Use of Class I antiarrhythmic drugs, including disopyramide, within 7 days prior to Screening
- 14) Use of ranolazine within 7 days prior to Screening
- 15) Use of concomitant treatment with drugs or products that are strong inhibitors or inducers of CYP3A (see [Appendix 9](#)) within 5- half-lives prior to Screening

- 16) Known hypersensitivity to study drug (GS-6615 or placebo), its metabolites, or formulation excipient

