8.6.3. Laboratory Evaluations

Selected laboratory data will be summarized by treatment group. Data and change from baseline at scheduled time points will be summarized.

Laboratory data will be listed. In addition, a separate listing of treatment-emergent laboratory abnormalities will be provided. Laboratory abnormalities will be defined relative to the normal range.

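### No by-arm laboratory table remains, and the treatment-emergent listing cannot flag worsening of a test that was already abnormal at baseline

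*SAP*

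**What the plan says.** Protocol 8.1.5 includes laboratory tests among the safety endpoints, and safety and tolerability is a secondary objective (Protocol 2, SAP 1.1). Protocol 8.6.3 planned three outputs:

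- tables, with change from baseline: "Selected laboratory data will be summarized by treatment group";
- a listing of all laboratory data;
- a further listing: "In addition, a separate listing of treatment-emergent laboratory abnormalities will be provided".

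The SAP, rewritten for a synoptic report after the sponsor stopped the trial, drops the tables. Section 7.10 says "Laboratory data, concomitant medication data, vital signs from CPET, and ECG overall assessments will not be summarized", and Section 7.2 now reads only "Laboratory data will be listed". The treatment-emergent listing stays, with this rule in Section 7.2.1: "Treatment-emergent laboratory abnormalities are defined as values that are normal at baseline (on or within the reference range bounds) and abnormal post-baseline". An abnormal value with a missing baseline also counts. No toxicity grades are assigned.

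On entry, Protocol 4.3, exclusion 11, bars "Abnormal liver function tests at Screening, defined as ALT or AST" above 2x ULN, or total bilirubin above 1.5x ULN. Values between ULN and those limits are eligible.

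**The concern.** Two losses combine. With the tables gone, nothing derived from laboratory values is counted by arm. The one derived flag that survives is blind to a test that was out of range at the start. A subject who enters with a modestly raised ALT and then has a large rise carries no flag, while a subject who moves just past the upper limit does.

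At stake is whether the report can answer a simple question about a safety endpoint: how many subjects per arm had a laboratory value beyond a stated threshold. A baseline abnormality precedes randomisation, so the omission should fall evenly on the arms by design. If the drug did raise a test, however, more of the unflagged rises would be on active drug, and the flagged counts would understate the difference.

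**Working it through.** The plan gives no laboratory rate or count, so there is no figure of its own to reproduce here.

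**Inputs.** Flag rule: SAP 7.2.1. Eligibility limits: Protocol 4.3, exclusion 11. Baseline: last record on or before first dose (SAP 3.7). The procedures tables in both documents schedule clinical laboratory samples at Screening but not at Randomization, so the Screening value that passed eligibility normally becomes baseline. Planned size: 180, 90 per arm (SAP 1.3).

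**Step 1, the rule applied.** For an upper limit, flag = (baseline missing or at most 1x ULN) and (post-baseline above 1x ULN).

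| Baseline (x ULN) | Post-baseline (x ULN) | Flagged |
|---|---|---|
| 1.0 | 1.05 | yes |
| 1.0 | 4 | yes |
| missing | 1.1 | yes |
| 1.2 | 4 | no |
| 1.5 | 8 | no |
| 1.8 | 6 | no |
| 2.0 | 10 | no |

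Every baseline in the last four rows is within the ALT/AST entry limit.

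**Step 2, how many subjects could be affected.** The documents give no share *s* with a raised but eligible liver test. Taking *s* as an assumption, the count is 180 x *s*:

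- *s* = 5%: 180 x 0.05 = 9 (4.5 per arm)
- *s* = 10%: 180 x 0.10 = 18 (9 per arm)
- *s* = 20%: 180 x 0.20 = 36 (18 per arm)

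These are subjects who cannot be flagged for that test. They are not missed cases.

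**Step 3, how many large rises might go unflagged.** Assume further that 5% of an arm of 90 has a large rise (90 x 0.05 = 4.5 subjects), and that subjects with a raised baseline have *k* times the risk of the others. The risk with a normal baseline is then *b* = 0.05 / ((1 - *s*) + *k* x *s*), and the unflagged number per arm is 90 x *s* x *k* x *b*.

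| *s* | *k* = 1 | *k* = 3 |
|---|---|---|
| 5% | 0.23 | 0.61 |
| 10% | 0.45 | 1.1 |
| 20% | 0.90 | 1.9 |

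For example, with *s* = 10% and *k* = 3, *b* = 0.05 / 1.2 = 0.0417, and 90 x 0.10 x 3 x 0.0417 = 1.1. So between about 0.2 and 1.9 of 4.5 cases per arm would be unflagged. That is small in number but can be a material share of a rare event.

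**Step 4, whether another output fills the gap.** The adverse events of special interest in SAP 7.1.7 cover cardiac failure, syncope and dizziness, and convulsions; none is hepatic. Laboratory adverse events are tabulated by preferred term and by investigator-assigned severity (SAP 7.1.6), not by multiple of ULN.

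**The case against.** The strongest reply is that this is an openly declared reduction. The trial was stopped early, the SAP was rewritten for a synoptic report, the change is stated in Section 7.10 and explained in the revision log, and Protocol 9.2.2 allows an abbreviated report. A data monitoring committee also reviewed safety during the trial. This stands: there is no hidden contradiction. It does not show that a synoptic report needs no laboratory table at all. SAP 1 keeps summaries for relevant safety measures, Sections 7.3 and 7.7 still tabulate vital signs and ECG thresholds by arm, and Table 3-4 still carries visit windows for laboratory data.

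A reader might infer that these subjects vanish from the safety record, or that no laboratory finding is available by arm. The documents do not support that:

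- Their values stay in the full listing.
- Protocol 7.1.3 requires an adverse event when an abnormality needs intervention or leads to a change in study drug, and Protocol 6.20 asks for one when the investigator finds the value clinically significant. Those events are tabulated by arm.
- The gap is per test: raised ALT at baseline does not stop a flag on another test.

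What these routes lack is a flag and a count at a fixed threshold.

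A reader might also infer that the treatment-emergent listing was brought in as a substitute for the tables. It was not; Protocol 8.6.3 planned it alongside them.

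Finally, a reader might see a liver signal in the Phase 1 report (Protocol 1.2.3): "An alanine aminotransferase (ALT) value of 4 times the upper limit of normal (ULN) was reported in one subject receiving the 30 mg dose", which is also the loading dose here. The same paragraph reports a placebo subject above 3x ULN. Both had normal bilirubin and returned to baseline within days, and single doses up to 60 mg were studied. Isolated elevations on both sides are a reason to count by arm, not evidence of toxicity.

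**Conclusion.** The point holds in a limited form. No laboratory-derived table by arm remains, and the stated flag gives a wrong result for any test abnormal at baseline: it misses 1.8x to 6x ULN and catches 1.0x to 1.05x. Such cases are left to an unflagged listing or to investigator reporting.

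The size cannot be fixed from the documents. The 9 to 36 subjects rest on an assumed share of 5% to 20% applied to the planned 180; the trial stopped early and the actual number is not given. The 0.2 to 1.9 unflagged cases per arm add an assumed 5% event rate and an assumed risk ratio of 1 to 3. This is a weakness of the reduced plan that is worth correcting because correction is cheap. It does not touch the efficacy analysis.

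**What to change.** 1. In SAP 7.2.1, also flag a post-baseline value that worsens materially, in the same direction, from an abnormal baseline. Set the margin in advance, for example a fixed multiple of the baseline value or the crossing of a fixed multiple of ULN. Flagging any increase at all would pick up changes such as 1.10x to 1.11x ULN, which are noise.
2. Add one descriptive table of n (%) per arm with a treatment-emergent abnormality by parameter, including a row for ALT or AST above 3x ULN and bilirubin in multiples of ULN. Since entry is capped at 2x ULN, crossing 3x from an eligible baseline means at least a 1.5-fold rise (3 / 2), so that row is not driven by trivial change.
3. Amend SAP 7.10 to match.

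The cost is one added derivation, because the SAP does not now express values as multiples of ULN, and one extra table in the synoptic report. No new data or tests are needed. SAP 2 places unblinding after the data are final, so the rule can be set before assignments are known.
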